10.1.5 Committees structure

10.1.5.1 Data monitoring committee

- A Data Monitoring Committee (DMC) will be appointed to monitor the safety and scientific integrity of this study. The DMC, independent from the Sponsor and the Investigators, is responsible for monitoring the safety of the study participants enrolled in the clinical trial on an on-going basis in order to provide, in a timely fashion, appropriate recommendations to the Sponsor.
- An early aggregated safety data review will be performed by the DMC, the goal of which is to allow for a cautious, approach to study intervention administration. The DMC has the possibility to request an ad-hoc meetings (teleconferences), clearly identifying the safety-related reason for such an additional meeting and taking account of the then current recruitment status and recruitment rate. At each DMC meeting during the conduct of the trial, the DMC makes a recommendation to the Sponsor/Steering Committee to continue the trial as planned, or with an amendment, or to terminate the trial. Details regarding the DMC are included in the DMC charter.
- Participant safety will be continuously monitored by the Sponsor’s internal safety review team, which includes safety signal detection at any time during the study.
- All safety data collected will be reviewed by the Sponsor’s internal safety team for agreement of next steps.
- In particular, data will be reviewed by the Sponsor for identification of the following events that would potentially contribute to a requirement to pause/stop the study.
 - Any deaths, regardless of causality
 - Any major bleeding events, including bleeding into a critical organ, life threatening or fatal bleeding
 - Other

10.1.6 Dissemination of clinical study data and results

Study participants

At the end of the clinical study, the Sponsor may publish the study results in scientific journal(s). As part of the review for publication, independent scientists may need to use “coded” data of all the study participants to independently verify the study’s results.

Sanofi shares information about clinical trials and results on publicly accessible websites, based on company commitments, international and local legal and regulatory requirements, and other clinical trial disclosure commitments established by pharmaceutical industry associations. These websites include ClinicalTrials.gov, euclinicaltrials.eu, and sanofi.com, as well as some national registries. For pediatric and adult trials, the results will generally be submitted/released 6 and 12 months respectively, after the end of the clinical trial worldwide (ie, the last active, participating country).

In addition, results from clinical trials in participants are required to be submitted to peer-reviewed journals following internal company review for accuracy, fair balance and intellectual property. For those journals that request sharing of the analyzable data sets that are reported in the publication, interested researchers are directed to submit their request to vivli.org.

Individual anonymized participant data and supporting clinical documents are available for request at vivli.org. While making information available we continue to protect the privacy of participants in our clinical trials. Details on data sharing criteria and process for requesting access can be found at this web address: vivli.org.

Professionals involved in the study or in the drug development program

Sanofi may publicly disclose, and communicate to relevant authorities/institutions, the funding, including payments and transfers of value, direct or indirect, made to healthcare organizations and professionals and/or any direct or indirect advantages and/or any related information or document if required by applicable law, by regulation or by a code of conduct such as the “EFPIA Code on Disclosure of Transfers of Value from Pharmaceutical Companies to Healthcare Professionals and Healthcare Organisations”.

10.1.7 Data quality assurance

- All participant data relating to the study will be recorded on printed or electronic CRF unless transmitted to the Sponsor or designee electronically (eg, laboratory data). The Investigator is responsible for verifying that data entries are accurate and correct by physically or electronically signing the CRF.
- Guidance on completion of CRFs will be provided in CRF Completion Instructions.
- The Investigator must permit study-related monitoring, audits, IRB/IEC review, and regulatory agency inspections and provide direct access to source data documents.
- Monitoring details describing strategy, including definition of study critical data items and processes (eg, risk-based initiatives in operations and quality such as risk management and

mitigation strategies and analytical risk-based monitoring), methods, responsibilities, and requirements, including handling of noncompliance issues and monitoring techniques (central, remote, or on-site monitoring) are provided in separate study documents.

- The Sponsor or designee is responsible for the data management of this study, including quality checking of the data.
- The Sponsor assumes accountability for actions delegated to other individuals (eg, contract research organizations).
- Records and documents, including signed ICFs, pertaining to the conduct of this study must be retained by the Investigator for 25 years after the signature of the final study report unless local regulations or institutional policies require a longer retention period. No records may be destroyed during the retention period without the written approval of the Sponsor. No records may be transferred to another location or party without written notification to the Sponsor.

10.1.8 Source documents

- Source documents provide evidence for the existence of the participant and substantiate the integrity of the data collected. Source documents are filed at the Investigator's site.
- Data reported on the CRF or entered in the eCRF that are transcribed from source documents must be consistent with the source documents or the discrepancies must be explained. The Investigator may need to request previous medical records or transfer records, depending on the study. Also, current medical records must be available.
- Definition of what constitutes source data can be found in the CRF Completion Guideline/ Instruction.
- The Investigator must maintain accurate documentation (source data) that supports the information entered in the CRF.
- Study monitors will perform ongoing source data verification to confirm that data entered into the CRF by authorized site personnel are accurate, complete, and verifiable from source documents; that the safety and rights of participants are being protected; and that the study is being conducted in accordance with the currently approved protocol and any other study agreements, ICH GCP, and all applicable regulatory requirements.

10.1.9 Study and site start and closure

First act of recruitment

The study start date is the date on which the clinical study will be open for recruitment of participants.

The first act of recruitment is the first site open and will be the study start date.

Study/Site termination

The Sponsor or designee reserves the right to close the study site or terminate the study at any time for any reason at the sole discretion of the Sponsor. Study sites will be closed upon study completion. A study site is considered closed when all required documents and study supplies have been collected and a study-site closure visit has been performed.

The Investigator may initiate study-site closure at any time, provided there is reasonable cause and sufficient notice is given in advance of the intended termination.

Reasons for study termination by the Sponsor, as well as reasons for the early closure of a study site by the Sponsor or Investigator may include but are not limited to:

- For study termination:
 - Information on the product leads to doubt as to the benefit/risk ratio
 - Discontinuation of further study intervention development
- For site termination:
 - Failure of the Investigator to comply with the protocol, the requirements of the IRB/IEC or local health authorities, the Sponsor's procedures, or GCP guidelines
 - Inadequate or no recruitment (evaluated after a reasonable amount of time) of participants by the Investigator
 - Total number of participants included earlier than expected

If the study is prematurely terminated or suspended, the Sponsor shall promptly inform the Investigators, the IECs/IRBs, the regulatory authorities, and any contract research organization(s) used in the study of the reason for termination or suspension, as specified by the applicable regulatory requirements. The Investigator shall promptly inform the participant and should assure appropriate participant therapy and/or follow-up.

10.1.10 Publication policy

- The results of this study may be published or presented at scientific meetings. If this is foreseen, the Investigator agrees to submit all manuscripts or abstracts to the Sponsor before submission. This allows the Sponsor to protect proprietary information and to provide comments.
- The Sponsor will comply with the requirements for publication of study results. In accordance with standard editorial and ethical practice, the Sponsor will generally support publication of multicenter studies only in their entirety and not as individual site data. In this case, a coordinating Investigator will be designated by mutual agreement.
- Authorship will be determined by mutual agreement and in line with International Committee of Medical Journal Editors authorship requirements.

10.2 APPENDIX 2: CLINICAL LABORATORY TESTS

- Screening tests will be performed by the local laboratory.
- For tests to be performed by the central laboratory: local laboratory results are only required in the event that the central laboratory results are not available in time for either study intervention administration and/or response evaluation. If a local sample is required, it is important that the sample for central analysis is obtained at the same time. Additionally, if the local laboratory results are used to make either a study intervention decision or response evaluation, the results must be recorded.
- Protocol-specific requirements for inclusion or exclusion of participants are detailed in [Section 5](#) of the protocol.
- Additional tests may be performed at any time during the study as determined necessary by the Investigator or required by local regulations.

Table 8 - Protocol-required laboratory tests

Laboratory tests	Parameters
Blood smear	Blood smear ^a
Hematology	
Platelet count^f
 
Red blood cell (RBC) count
 
Hemoglobin
 
Hematocrit
 
RBC indices:
 
Mean corpuscular volume (MCV)Mean corpuscular hemoglobin (MCH)Mean corpuscular hemoglobin concentration (MCHC)%Reticulocytes 
White blood cell (WBC) count with differential:
 
NeutrophilsLymphocytesMonocytesEosinophilsBasophils
Coagulation parameters	
Prothrombin time (PT)
 
Activated partial thromboplastin time (aPTT)

Clinical chemistry ^b	
Blood urea nitrogen (BUN)
 
Creatinine
 
Glucose
 
Chloride
 
Potassium
 
Sodium
 
Calcium

Laboratory tests	Parameters
	Aspartate aminotransferase (AST) Alanine aminotransferase (ALT) Alkaline phosphatase ^c Total and direct bilirubin Total protein
Other screening tests	COVID test (SARS-CoV-2 RT-PCR or antigen test) Serology (HIV antibody, hepatitis B surface antigen [HBsAg], and hepatitis C virus antibody) Pregnancy test: Highly sensitive urine human chorionic gonadotropin (hCG) pregnancy test (as needed for women of childbearing potential). If a urine test cannot be confirmed as negative (eg, an ambiguous result), a serum pregnancy test is required.
Organ damage markers	Cardiac troponin I (cTnI) ^f Creatinine ^{d,f} Lactate dehydrogenase (LDH) ^f
ADAMTS13	ADAMTS13 activity Anti-ADAMTS13 antibody

NOTES:

- a Blood smear that will be assessed by a local laboratory.
- b Details of liver chemistry stopping criteria and required actions and follow-up are given in [Section 7.1.2 Liver Chemistry Stopping Criteria](#) and Appendix 6 ([Section 10.6](#)) Liver safety: Suggested actions and follow-up assessments. All events which may indicate severe liver injury (possible Hy's Law) must be reported to Sponsor in an expedited manner (excluding studies of hepatic impairment or cirrhosis).
- c If alkaline phosphatase is elevated, consider fractionating.
- d Serum creatinine will be tested as part of the clinical chemistry tests.
- e Baseline ADAMTS13 activity test will be done locally, and also a sample will be sent to central laboratory for ADAMTS13 activity and antibody tests. Subsequent ADAMTS13 activity and antibodies samples will be tested by central laboratory.
- f Platelet count, LDH, cTnI, and creatinine should be assessed locally throughout the entire hospitalization but baseline, 24-hour, 48-hour, 60-hour, and subsequent daily samples during the hospitalization must be assessed centrally as well.

Investigators must document their review of each laboratory safety report.

10.3 APPENDIX 3: AES AND SAES: DEFINITIONS AND PROCEDURES FOR RECORDING, EVALUATING, FOLLOW-UP, AND REPORTING

10.3.1 Definition of AE

AE Definition

- An AE is any untoward medical occurrence in a patient or clinical study participant, temporally associated with the use of study intervention, whether or not considered related to the study intervention.
- NOTE: An AE can therefore be any unfavorable and unintended sign (including an abnormal laboratory finding), symptom, or disease (new or exacerbated) temporally associated with the use of study intervention.

Definition of unsolicited and solicited AE

- An unsolicited adverse event is an adverse event that was not solicited and that is communicated by a participant/legally authorized representative (LAR) who has signed the informed consent. Unsolicited AEs include serious and nonserious AEs.
- Potential unsolicited AEs may be medically attended (ie, symptoms or illnesses requiring a hospitalization, emergency room visit, or visit to/by a health care provider). The participant/legally authorized representative (LAR) will be instructed to contact the site as soon as possible to report medically attended event(s), as well as any events that, though not medically attended, are of participant/legally authorized representative (LAR) concern. Detailed information about reported unsolicited AEs will be collected by qualified site personnel and documented in the participant's records.
- Unsolicited AEs that are not medically attended nor perceived as a concern by the participant/legally authorized representative (LAR) will be collected during an interview with the participant/legally authorized representative (LAR) and by review of available medical records at the next visit.
- Solicited AEs are predefined local and systemic events for which the participant is specifically questioned.

Events meeting the AE definition

- Any abnormal laboratory test results (hematology, clinical chemistry, or urinalysis) or other safety assessments (eg, ECG, radiological scans, vital signs measurements), including those that worsen from baseline, considered clinically significant in the medical and scientific judgment of the Investigator (ie, not related to progression of underlying disease), eg:
 - Symptomatic and/or
 - Requiring either corrective treatment or consultation, and/or
 - Leading to IMP discontinuation or modification of dosing, and/or
 - Fulfilling a seriousness criterion, and/or
 - Defined as an AESI

- Exacerbation of a chronic or intermittent pre-existing condition including either an increase in frequency and/or intensity of the condition.
- New condition detected or diagnosed after study intervention administration even though it may have been present before the start of the study.
- Signs, symptoms, or the clinical sequelae of a suspected drug-drug interaction.
- Signs, symptoms, or the clinical sequelae of a suspected overdose of either study intervention or a concomitant medication.
- Lack of efficacy or failure of expected pharmacological action per se will not be reported as an AE or SAE. Such instances will be captured in the efficacy assessments. However, the signs, symptoms, and/or clinical sequelae resulting from lack of efficacy will be reported as AE or SAE if they fulfill the definition of an AE or SAE.

Events NOT meeting the AE definition

- Any clinically significant abnormal laboratory findings or other abnormal safety assessments that are associated with the underlying disease, unless judged by the Investigator to be more severe than expected for the participant's condition.
- The disease/disorder being studied or expected progression, signs, or symptoms of the disease/disorder being studied, unless more severe than expected for the participant's condition.
- Medical or surgical procedure (eg, endoscopy, appendectomy): the condition that leads to the procedure is the AE.

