8.1.2 Clinically significant TTP events

Clinically significant TTP events will be assessed at the time points indicated in the SoA ([Section 1.3](#)).

Date of onset, severity, and outcome of following parameters will be collected:

- Neurological
- Cardiovascular
 - Elevated cardiac troponins I (cTnI) (value and local upper limit of reference range)
 - Acute myocardial infarction (ECG finding)
 - Conduction abnormality (ECG finding)
 - Repolarization abnormality (ECG finding)
 - Heart failure (severity)
 - Other (to be specified)
- Renal
- Exacerbation of TTP
- Relapse of TTP
- Death due to TTP
- Other (to be specified)

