8.1.3 Neurological assessment and Glasgow Coma Scale

At screening, the neurologic status of the adult subjects will be assessed using the Glasgow Coma Scale (GCS), a neurological scale that measures the conscious state of the subject. The GCS is to be assessed within 2 hours prior to enrollment. The best eye, verbal and motor responses will be scored according to the scale, and the separate scores added up to obtain the final score, ranging from 3 to 15. An example of the GCS is provided in [Section 8.1.3.1](#).

At all other time points defined in the SoA ([Section 1.3](#)), the neurological status of the subjects will also be assessed by examination of the neurological system and presence (including severity) or not of the following: coma, stupor, seizures, disorientation/confusion, hemiparesis/-plegia, focal deficit, agitation, and dysarthria (primarily physical examination and as per standard of care and by Investigator's judgement: electroencephalogram [EEG], magnetic resonance imaging [MRI], etc).

In case coma or stupor are present, the GCS needs to be completed.

The Investigator will determine whether the observed abnormality is to be considered as a clinically significant TTP event.

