3.6.2 Adverse events

General common rules for adverse events

All AEs will be coded to a lower-level term (LLT), preferred term (PT), high-level term (HLT), high-level group term (HLGT), and associated primary system organ class (SOC) using the version of Medical Dictionary for Regulatory Activities (MedDRA) currently in effect at Sanofi at the time of database lock.

The AEs will be analyzed in the following 3 categories:

- Pre-treatment AEs: AEs that developed, worsened, or became serious during the pre-treatment period.
- Treatment-emergent adverse events (TEAEs): AEs that developed, worsened, or became serious during the TE period.
- Post-treatment AEs: AEs that developed, worsened, or became serious during the post-treatment period.

Similarly, the deaths will be analyzed in the pre-treatment, TE, and post-treatment periods.

The primary focus of AE reporting will be on TEAEs. Pre-treatment and post-treatment AEs will be described separately.

An AE with incomplete or missing date/time of onset (occurrence, worsening, or becoming serious) will be classified as a TEAE unless there is definitive information to determine it is a pre-treatment or a post-treatment AE.

If the assessment of the relationship to IMP is missing for an AE, this AE will be assumed as related to IMP, ie, to caplacizumab.

If the severity is missing for 1 of the TE occurrences of an AE, the severity will be imputed with the maximal severity of the other occurrences. If the severity is missing for all the occurrences, the severity will be left as missing.

Multiple occurrences of the same event in the same participant will be counted only once in the tables within a treatment phase.

The AE tables will be sorted as indicated in [Table 4](#).

Table 4 - Sorting of AE tables

AE presentation	Sorting rules
SOC and PT	By the internationally agreed SOC order and decreasing frequency of PTs ^{a, b}

a Sorting will be based on the overall incidence.

b The table of all TEAEs presented by SOC and PT will define the presentation order for all other tables (eg, treatment-emergent SAE) presented by SOC and PT, unless otherwise specified.

Analysis of all adverse events

The overview of TEAE with the details below will be generated:

- Any TEAE
- Any TE SAE
- Any TEAE leading to death
- Any TEAE leading to permanent discontinuation of caplacizumab
- Any TEAE leading to caplacizumab interruption
- Any AESI
- Any AESI related to IMP
- Any TEAE related to IMP
- Any SAE related to IMP

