- The values resulting from these derivations will be the values used for the graphical representation of platelet, LDH and ADAMTS13 activity from Day 4.

Consecutive laboratory assessments are considered as 'consecutive visits' for efficacy endpoints.

A participant could potentially have missing laboratory assessment data, however, remission could still be confirmed at a subsequent laboratory value. In the case there is inadequate information to determine the remission status of a participant by the end of the study, the participant will be treated as not having achieved remission.

Clinical evidence of new or progressive ischemic organ injury

Clinical evidence of new or progressive ischemic organ injury is defined as any presence of following clinically significant iTTP event:

- Neurological event
- Elevated cardiac troponins
- Acute myocardial infarction
- Conduction abnormality
- Repolarization abnormality
- Heart failure
- Clinically significant renal event

which will be identified from the checkboxes in the "Clinically Significant TTP Event" eCRF form.

Exacerbation of TTP, Relapse of TTP and Other event will not be considered as clinical evidence of new or progressive ischemic organ injury.

Sustained Clinical Response

Sustained Clinical response is defined by the concomitance of the 3 following criteria for at least 2 consecutive visits (starting from D2):

- platelet count $\geq 150 \times 10^9/L$
- LDH $< 1.5 \times ULN$
- no clinical evidence of new or progressive ischemic organ injury

Remission

Remission is defined as (1) a sustained Clinical response (see above) associated with (2) Clinical remission or (3) Complete ADAMTS13 Remission, whichever occurs first, and defined as:

- Clinical remission: No TPE (*Plasma Exchange* form) and no anti-VWF therapy (Caplacizumab treatment) for ≥ 30 days (from the date that Clinical Response is achieved).
- Complete ADAMTS13 Remission: The attainment of ADAMTS13 activity level $\geq 50\%$ for at least 2 consecutive visits (starting from D2).

Time to event

For each of below time to event, in case of no observation of the event or death, the censoring date will be defined as the last non-missing value of the analyzed parameter (platelet count, LDH....) if any, else as the start date of treatment (defined as first caplacizumab administration [whatever marketed or study IMP]).

- Time to platelet count response will be calculated as follow:

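### Non-major bleeding regarded as an expected sign of iTTP can be left out of the AE data, and the readable SAP has no summary of the scheduled bleeding assessment that would show it

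*Protocol*

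**What the plan says.** Protocol 10.3.1, in its list of events that are not AEs, removes "expected progression, signs, or symptoms of the disease/disorder being studied, unless more severe than expected". A companion bullet removes abnormal laboratory results "or other abnormal safety assessments that are associated with the underlying disease, unless judged by the Investigator to be more severe than expected". On the inclusion side, the same section makes abnormal safety assessments AEs when they are "considered clinically significant in the medical and scientific judgment of the Investigator (ie, not related to progression of underlying disease"), for instance when symptomatic or needing treatment. Neither list makes an exception for bleeding.

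Protocol 2.2 ties mucocutaneous bleeding to the thrombocytopenia of iTTP. Protocol 2.3.1 names bleeding as the main risk of caplacizumab in this disease.

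The schedules in Protocol 1.3.1 to 1.3.3 place a dedicated bleeding assessment at screening, on Day 1, on every hospital day, weekly during treatment, at early discontinuation and at every follow-up visit. Protocol 10.1.7 says "All participant data relating to the study will be recorded on printed or electronic CRF" unless sent electronically, so the result should exist as data. The CRF itself is not among the documents.

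SAP 3.6.2 builds its bleeding table from treatment-emergent events in the Haemorrhage SMQ and takes AESIs, including major bleeding, from a tick box on the AE page. SAP 3.6.3.1 lists laboratory variables, vital signs, ECG, organ damage markers and ADAMTS13. The bleeding assessment is not on that list.

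**The concern.** The occurrence of AEs, SAEs and AESIs is a secondary endpoint, and bleeding is the event a reader will look for first. For that event, disease sign and drug effect look alike at the bedside. The AE definition gives the Investigator a legitimate reason to record nothing, mainly while platelets are still low and iTTP is the obvious explanation.

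There is no control arm under the same rule, so an omission does not cancel out. It can only lower the bleeding figures of the one regimen being described. The study already collects an independent record against which the AE table could be checked, but the readable plan does not use it.

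**Working it through.** **Step 1: how far disease sign and drug risk overlap.** The schedule footnotes give six examples for the bleeding assessment: petechiae, bruises, epistaxis, hematuria, menorrhagia and gastrointestinal bleeding. Protocol 2.2 lists five of these six (all but menorrhagia) as ways iTTP presents. Epistaxis is also one of the two most common bleeding events on caplacizumab in Protocol 2.3.1.

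**Step 2: routes from a bleeding finding into the AE data.**
- *General AE definition (10.3.1).* It covers any untoward occurrence regardless of relationship and favours reporting. The specific exclusion in the same section cuts the other way.
- *Abnormal safety assessments (10.3.1).* This route depends on Investigator judgement and is limited to findings not due to the disease.
- *Record review (10.3.1).* Unsolicited events that were not medically attended are picked up by interview and by review of records. The event must still qualify as an AE.
- *Hospital complications (10.3.2).* These are called AEs without qualification. The sentence sits inside the hospitalization criterion for SAEs and does not say whether an expected disease sign is a complication.
- *Causality (10.3.3).* A known response pattern of the drug points to a related event, and mucocutaneous bleeding is that pattern. This section applies to events already recorded as AEs.
- *Physical examination (8.2.1).* Clinically significant findings must be reported. The examination is scheduled on Day 1 and then at weekly visits from Day 8 (±3 days), so the next one falls 4 days (8 − 3 − 1) to 7 days (8 − 1) or more after Day 1. Platelet recovery in Protocol 2.3.2 has medians of 2.69 and 2.97 days on caplacizumab in the two earlier trials, and 84 h / 24 = 3.5 days (maximum 96 h / 24 = 4.0 days) in the case series without plasma exchange.
- *AESI (8.3.6).* Major bleeding only.
- *Clinically significant TTP event form (8.1.2).* "Date of onset, severity, and outcome of following parameters will be collected": neurological, cardiovascular, renal, exacerbation, relapse, death and other. There is no bleeding item.

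Major, serious and worse-than-expected bleeding, and bleeding not put down to iTTP, is captured. What is left is non-major bleeding attributed to iTTP, for which reporting is likely but not required.

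**Step 3: effect on the tables.** SAP 3.6.2 states "Multiple occurrences of the same event in the same participant will be counted only once in the tables within a treatment phase". The percentage with bleeding therefore falls only if a participant's only bleed is missed. The number of events, which SAP 3.6.2 also reports, falls with every missed bleed.

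**Step 4: scale.** The only bleeding rates in the documents are those of Protocol 2.3.1, and they reproduce: 17/106 = 16.0% (gingival) and 31/106 = 29.2% (epistaxis). Assume that the epistaxis rate applies to 61 treated participants: 61 × 31/106 = 17.8, say 18.

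| Only-bleeds missed | Observed | Rate |
|---|---|---|
| 0 | 18/61 | 29.5% |
| 1 | 17/61 | 27.9% |
| 2 | 16/61 | 26.2% |
| 3 | 15/61 | 24.6% |

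Each participant is 1/61 = 1.6 points, and three are 3/61 = 4.9 points. For comparison, the 95% Wilson interval for 18/61 is 19.6% to 41.9%.

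The number missed has to be assumed. As one illustration, spread onset evenly over treatment and lose every bleed before platelet recovery:
- 84 days of treatment (12 × 7, the maximum) with a 2.69-day window: 2.69/84 = 3.2%, and 17.8 × 3.2% = 0.6 participants.
- 28 days of treatment (my assumption, not in the documents) with a 4.0-day window: 4.0/28 = 14.3%, and 17.8 × 14.3% = 2.5 participants.

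**The case against.** The strongest reply is that the protocol, read as a whole, steers Investigators toward reporting. Complications in hospital are AEs, records are reviewed, a worsening pre-existing condition is an AE, and an Investigator who knows the drug's pattern will rarely put a new post-dose bleed down to iTTP alone. Severity is weighed against the participant's own condition, and clinically significant active bleeding is excluded at entry (E 05), so new bleeding may well count as worse than expected. In the earlier iTTP trials bleeding was the most commonly reported AE in both groups (Protocol Table 1), and nothing in the documents shows bleeds being left out. Much of this stands. It makes reporting likely and the loss probably small. It does not close the gap, because none of these clauses says that a finding on the bleeding assessment is an AE despite the exemption. The AE rules of the earlier trials are not given either.

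It is also fair that exempting expected disease signs is a legitimate choice, that the analyses are descriptive with no success criterion, and that the primary endpoint is untouched. That limits the weight of the point. Parts of SAP 3.4 and 3.7 are redacted and the CRF instructions are separate documents, so the claim covers the readable text only.

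A reader might infer that early bleeding will routinely go unrecorded because nothing requires it. The clauses above do not support that. A reader might also take the 0.6 to 2.5 participants in the working as a ceiling. It is not one: it rests partly on medians, which about half of participants exceed, on a median from a trial in which all had prior plasma exchange, on an assumed 28-day course, and on even onset. Clustering of bleeds while platelets are low would raise it, and partial reporting would lower it.

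**Conclusion.** The point holds as a minor one. Protocol 10.3.1 permits non-major bleeding regarded as an expected sign of iTTP to stay out of the AE data. The readable SAP has no second count that would reveal it. The bias, if any, runs in one direction, toward a safer-looking regimen. Its size cannot be derived from the documents and is probably small. At 1.6 points per participant (assuming 61 treated), a few missed only-bleeds would move the rate by less than its sampling uncertainty, while event counts could fall further. A reader might conclude that the AE definition must be rewritten now. The documents do not support that: enrolment began in November 2022, and a new definition would put two recording rules into one small arm.

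**What to change.** Add to SAP 3.6.3 a Safety-population table or listing of participants with new or worsened findings on the scheduled bleeding assessment versus baseline during the treatment-emergent period, reconciled participant by participant with the Haemorrhage SMQ table. Name the in-hospital days explicitly, because SAP 5.4 drops hospitalization-visit laboratory, vital-sign and ECG data from by-visit analyses and a programmer might carry that convention over. Cover all participants, including those already enrolled.

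Optionally, send sites a note that bleeding that starts or worsens after the first caplacizumab dose should be reported as an AE, with the question of iTTP or drug handled under causality in Protocol 10.3.3.

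The cost is one extra output from an assessment already scheduled, provided that the CRF holds its result. The downside is a bleeding figure that may be somewhat higher and will include disease-related bleeds that a single arm cannot separate from drug effect. The table should say so in a footnote.
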